12.2.7 Determination of subjects for analysis

All subjects with at least one attempted ablation procedure with the Phased RF system where at least one investigational catheter was deployed into the left atrium and have completed at least 30 days of post-procedure follow-up will be included in the analysis. Additionally, all subjects with a procedure and/or device related stroke as classified by the CEC with a symptom onset date within 30 days of a procedure where a Phased RF catheter was placed in the left atrium will be included in the analysis regardless of whether the subject has less than 30 days of post-procedural follow-up.

In the rare instance where a subject has a non-investigational ablation catheter placed in the left atrium, the subject will be excluded from the analysis of the primary objective. However, a summary of all peri-procedural AEs will be provided for any subject excluded from the primary analysis.

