7.15 Permissible Retreatment Ablation Procedure

All study subjects may have one reablation procedure with the Phased RF System within 180 days of their index ablation procedure under this protocol if the following criteria are met:

- Subject has not completed the 6-month follow-up visit
- Recurrent AF/AFL that cannot be controlled with antiarrhythmic drugs and/or cardioversion
- The subject has not had any other ablation procedure in the left atrium since first Phased RF ablation
- Subjects undergoing a retreatment procedure are willing to be followed for 6-months following their retreatment procedure, or until official study closure defined as when Medtronic and/or regulatory requirements have been satisfied per the Clinical Investigational Plan, whichever occurs first. Medtronic will provide a new set of target visit dates following notification of a retreatment procedure as described in section 7.6.

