12.2.5 Experimental design and analysis methods

This study is a prospective, unblinded, multi-center, worldwide clinical study designed to evaluate the procedure and/or device related peri-procedural stroke rate within 30 days of an ablation procedure with the Phased RF System. The study will be considered successful if the primary objective is met. A single decision regarding study success will be made once all subjects with a Phased RF ablation procedure have had the opportunity for a reablation procedure (completed the 6-month visit) or completed the 30-day post-reablation visit if a reablation is required. Alternatively, the study may stop early for futility if more than six (6) procedure and/or device related peri-procedural strokes occur prior to completing enrollment.

For computing the peri-procedural stroke rate, the denominator will be all subjects with at least one ablation procedure attempt where at least one of the Phased RF catheters was deployed into the left atrium and have at least 30 days of post-

procedure follow-up. Also, subjects who have a procedure and/or device related peri-procedural stroke as classified by the CEC with symptom onset date within 30 days of a Phased RF ablation procedure will be included. The numerator for the stroke rate will be all subjects included in the denominator that had a procedure and/or device related stroke as classified by the CEC with a symptom onset date within 30 days of a Phased RF ablation procedure. The null hypothesis will be rejected in favor of the alternative if the observed stroke rate is less than 1.8% and the exact one-sided upper 95% confidence interval is less than 3.5%.

Additionally, a one-sided exact p-value will be computed for comparing the observed stroke rate to the performance goal of 3.5%.

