12.2.8 Missing data

The impact of missing data on the analysis of this objective is expected to be small since only a 30 day post-ablation follow-up period is required. However, missing data could arise if a subject undergoes a Phased RF ablation procedure, does not have procedure and/or device related peri-procedural stroke, and exits the study

prior to their 30 day post-procedure visit. These subjects will not be included in the primary analysis cohort, but a tipping point analysis will be employed to determine the impact of the missing data on the observed stroke rate should the issue of missing data arise.

Another potential source of missing data comes from subjects that do not have a stroke following the index procedure, but exit the study following the 30-day post-index ablation visit, but prior to the 6-month visit or a reablation procedure. These subjects are included in the primary analysis as not having a stroke since no stroke was observed following the index ablation procedure. However, a tipping point analysis will be conducted to determine the plausibility these subjects could change the outcome of the study across a range of reablation rates and reablation stroke rates.

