### 3.2.2 Definition of Procedure and/or Device Related Stroke

Procedure and/or device related strokes are defined as events classified by the Clinical Events Committee (CEC) meeting all of the requirements in Table 5 in the VICTORY AF CIP (version 5). Specifically, the stroke must have a symptom onset date within 30 days of an ablation procedure where at least one phased RF catheter is deployed into the left atrium (i.e. placed in the left atrium with Phased RF energy delivered) and be considered related to the procedure and/or device by the CEC.

Specifically, in the Medtronic use only CRF (MDT ADVERSE EVENT), the following fields must be checked in relation to the CEC determination:

- Adverse Event is denoted neurological related with a diagnosis of “stroke”
- Adverse Event is denoted as Related to the Phased RF study procedure and/or related to one or more of the following system components: PVAC, PVAC GOLD, MAAC, MASC, or Medtronic GENius™ Multi-Channel RF Generator
- Adverse Event is denoted as “Yes” for meeting the periprocedural definition

Additionally, the following values are required on the relevant procedure CRF (treatment or reablation) to meet the primary endpoint:

- Time of initial Phased RF Catheter deployment in left atrium must be non-missing
- At least one record of Phased RF energy delivery must be present in the PVAC/PVAC GOLD, MAAC, and/or MASC ablation log CRF forms
- Non-investigation catheter use in the left atrium must NOT be checked
- The onset date of the stroke must be no more than 30 days following the index procedure (if stroke occurs prior to any reablation procedure) or no more than 30 days following a reablation procedure if stroke occurs following a reablation procedure.

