### 3.2.5 Determination of Subjects for Analysis

All subjects with at least one attempted ablation procedure with the Phased RF system where at least one investigational catheter was deployed into the left atrium (i.e. placed in the left atrium with Phased RF energy delivered) and have completed at least 30 days of post-procedure follow-up will be included in the analysis. Additionally, all subjects with a procedure and/or device related stroke as classified by the CEC with a symptom onset date within 30 days of a procedure where a Phased RF catheter was deployed in the left atrium will be included in the analysis regardless of whether the subject has less than 30 days of post-procedural follow-up.

In the rare instance where a subject has a non-investigational ablation catheter placed in the left atrium, the subject will be excluded from the analysis of the primary objective. However, a summary of all peri-procedural adverse events (AEs) will be provided for any subject excluded from the primary analysis.

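### The primary stroke analysis drops Phased RF-treated subjects who also had a non-study left-atrial ablation catheter, and no visible analysis tests the success criteria with them restored

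*Protocol*

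**What the plan says.** **The exclusion.** On the primary analysis, Protocol 12.2.7 says: "In the rare instance where a subject has a non-investigational ablation catheter placed in the left atrium, the subject will be excluded from the analysis". SAP 3.2.5 has the same rule: "the subject will be excluded from the analysis of the primary objective". Neither makes an exception for a subject who had a stroke.

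**The endpoint.** SAP 3.2.2 first lists the CEC findings needed for a stroke to count, then adds that "the following values are required on the relevant procedure CRF (treatment or reablation) to meet the primary endpoint". One of those values is "Non-investigation catheter use in the left atrium must NOT be checked". A stroke that the CEC has found related and periprocedural is therefore still barred if that box is checked.

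**The general definitions.** Protocol 12.2.5 says "the denominator will be all subjects with at least one ablation procedure attempt where at least one of the Phased RF catheters was deployed". Deployment must be in the left atrium, and at least 30 days of follow-up are needed; subjects with a CEC-classified related stroke within 30 days are added. SAP 3.2.3 is similar and also requires that Phased RF energy was delivered. Neither mentions the exclusion, and neither does the stroke definition in Protocol Table 5.

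**What happens to excluded subjects.** Protocol 12.2.7 promises that "a summary of all peri-procedural AEs will be provided for any subject excluded from the primary analysis". For subjects who exit before the 30-day visit, Protocol 12.2.8 says "a tipping point analysis will be employed to determine the impact of the missing data on the observed stroke rate"; a second tipping point analysis covers subjects who exit later but before 6 months or a reablation. Neither covers subjects removed for catheter use.

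**The concern.** The population is fixed partly by what the operator does once the subject has been exposed to the device. In a single-arm, unblinded safety study there is no comparator in which the same selection would occur. If another catheter tends to be used in harder procedures, the excluded subjects may also differ in stroke risk; the documents give no data on this.

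The time scope is also open. Protocol 12.2.7 and SAP 3.2.5 set no limit, whereas SAP 3.2.2 ties the condition to the relevant procedure form. One condition for retreatment in Protocol 7.15 is "The subject has not had any other ablation procedure in the left atrium since first Phased RF ablation", so the protocol foresees that a subject might have such an ablation. It does not say whether a later non-study ablation removes a result already observed.

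The stake is the single success decision. It rests on very few events, and a list of adverse events does not tell the reader whether both criteria would still be met with these subjects included.

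**Working it through.** **Inputs.** Success needs an observed rate below 1.8% and an exact one-sided 95% upper bound below 3.5% (Protocol 12.2.2). The target is 300 subjects and the assumed true rate is 1.3% (Protocol 12.2.6). The number excluded and their relative risk are not given. I assume 3 or 6 excluded (about 1% or 2%) at equal or double risk.

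**1. Stroke limit.** For x strokes in n subjects, upper bound = 95th percentile of Beta(x+1, n−x).

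| x/n | Rate | Upper bound | Result |
|---|---|---|---|
| 5/297 | 1.68% | 3.507% | fail |
| 5/300 | 1.67% | 3.472% | pass |
| 6/301 | 1.99% | 3.896% | fail |
| 6/335 | 1.79% | 3.504% | fail |
| 6/336 | 1.79% | 3.494% | pass |

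The limit is 4 strokes for n = 280 to 297, 5 for n = 298 to 335, and 6 at n = 336.

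**2. The plan's own figures.** Power at n = 300 is P(X ≤ 5). This gives 91.7% at a true rate of 1% (plan: 90%), 80.2% at 1.3% (80%) and 54.6% at 1.8% (55%). Type I error at 3.5% is 4.76% (plan: below 5%). The figures reproduce.

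**3. Weight at the boundary.** At 1.3%, P(X = 5) = 15.3%, and 15.3/80.2 = 19% of passing results sit exactly at 5/300.

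**4. What does 300 count?** Protocol 6.1 and the report cutoff in SAP 3.1.4.1 refer to 300 ablated subjects, which would include those later excluded. Protocol 1.11 and 12.2.6 point to 300 evaluable subjects. Both readings follow. X is strokes among retained subjects and Y strokes among excluded subjects.

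**5. Reading A: 300 retained, m excluded on top.** For m up to 35 the limit is 5 both for 300 and for 300 + m. Adding subjects cannot lower the stroke count, so exclusion can turn a fail into a pass but never a pass into a fail. For an overall rate p, excluded share f and relative risk RR, the retained rate is r = p/((1−f) + f·RR) and the excluded rate is r·RR. P(fail to pass) = P(X ≤ 5 and X + Y > 5):

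| True rate | RR | m = 3 | m = 6 |
|---|---|---|---|
| 1.3% | 1 | 0.60% | 1.21% |
| 1.3% | 2 | 1.18% | 2.33% |
| 3.5% | 1 | 0.29% | 0.56% |
| 3.5% | 2 | 0.59% | 1.18% |

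Type I error at 3.5% is 4.76% at equal risk, 5.06% and 5.38% at double risk, and 4.46% and 4.18% if the excluded subjects have no strokes.

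**6. Reading B: 300 ablated, m of them excluded.** With 297 or 294 retained the limit is 4, against 5 for all 300. A pass becomes a fail when X = 5 and Y = 0; a fail becomes a pass only when X ≤ 4 and X + Y ≥ 6. At 1.3% and equal risk:

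- m = 3: pass to fail = P(X = 5 | 297) × 0.987³ = 15.14% × 96.15% = 14.6%; fail to pass = 0.01%.
- m = 6: pass to fail = P(X = 5 | 294) × 0.987⁶ = 14.97% × 92.45% = 13.8%; fail to pass = 0.05%.

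Type I error with 3 excluded is 2.1% at equal risk, against 4.8% without exclusion.

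**The case against.** The rule is pre-specified, called rare in both documents, and part of a design that the SAP says was developed with FDA consultation. It confines the rate to procedures done with Phased RF catheters alone, which is a legitimate aim when a stroke could otherwise be due to two devices. There is also a disincentive: exclusive use of Phased RF catheters in the left atrium is a condition of acute success, and acute success is required for 6-month success, so another catheter costs the subject both effectiveness endpoints. Any stroke in an excluded subject would appear in the adverse event summary, and one could add it to the count by hand. Finally, 5/300 against 6/301 describes any single stroke at any exact-binomial limit.

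Most of this stands, and it keeps the point modest. It does not replace a stated analysis. The summary is not tied to the success criteria, and a hand calculation after the result is known invites dispute over one event. The missing cross-reference in Protocol 12.2.5 and SAP 3.2.3 is only editorial, since the specific rule can be read as governing the general one.

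A reader might infer two stronger things. One is that the exclusion always favours success. That holds under Reading A only, and the documents do not settle which reading applies. The other is that strokes are concealed, or that no restoring analysis exists anywhere. The summary contradicts the first of these. On the second, Protocol 12.2 shows no such analysis, but SAP 3.2.3 ends in redacted text and later SAP pages are redacted, so a SAP-only analysis cannot be ruled out.

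**Conclusion.** The point holds as a gap that should be closed, not as a fatal flaw. Phased RF-treated subjects can leave both numerator and denominator because of an event during or after exposure, even with a CEC-confirmed related stroke, and no visible analysis shows whether the two criteria survive their return.

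If use is rare, the expected anti-conservative effect is small: at most 2.3% at a true rate of 1.3% under Reading A, with type I error at 3.5% no higher than 5.4% over the assumed range. Under Reading B the rule mainly works against the sponsor, because losing even 3 of 300 subjects moves the limit from 5 to 4. No general claim about the direction of bias is justified. These sizes rest on assumed numbers excluded and assumed relative risks. The limits and the boundary examples do not.

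**What to change.** - **Added analysis.** In Protocol 12.2.7 and SAP 3.2.5, pre-specify that the stroke rate and both success criteria (below 1.8%, and exact upper bound below 3.5%) are also computed with these subjects restored. The set is every subject who meets the SAP deployment definition (catheter in the left atrium and Phased RF energy delivered) and the existing condition in Protocol 12.2.5 and SAP 3.2.3: at least 30 days of follow-up, or a CEC-classified related stroke within 30 days. Non-study catheter use is disregarded, and the corresponding checkbox condition in SAP 3.2.2 does not apply. Keeping the follow-up condition matters: without it, stroke-free early exits would enter the denominator and the comparison would no longer isolate the exclusion.
- **Reporting.** Show it beside the primary result, and address any disagreement in the conclusion.
- **Scope.** State in Protocol 12.2.7 and SAP 3.2.2 and 3.2.5 whether the exclusion covers only study procedures or also later ablations. Cross-reference it in Protocol 12.2.5 and SAP 3.2.3.

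The cost is wording and one computation. SAP 3.2.2 shows that the forms already record non-study catheter use and the CEC determination, so no new data are needed. The added rate may be slightly less favourable, and a stroke partly due to the other catheter may count in it. The primary analysis is unchanged, and the added analysis is informative under either reading of the 300.

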12.2.8 Missing data

The impact of missing data on the analysis of this objective is expected to be small since only a 30 day post-ablation follow-up period is required. However, missing data could arise if a subject undergoes a Phased RF ablation procedure, does not have procedure and/or device related peri-procedural stroke, and exits the study

prior to their 30 day post-procedure visit. These subjects will not be included in the primary analysis cohort, but a tipping point analysis will be employed to determine the impact of the missing data on the observed stroke rate should the issue of missing data arise.

Another potential source of missing data comes from subjects that do not have a stroke following the index procedure, but exit the study following the 30-day post-index ablation visit, but prior to the 6-month visit or a reablation procedure. These subjects are included in the primary analysis as not having a stroke since no stroke was observed following the index ablation procedure. However, a tipping point analysis will be conducted to determine the plausibility these subjects could change the outcome of the study across a range of reablation rates and reablation stroke rates.

12.2.9 Pre-specified Subgroup analyses

The procedure and/or device related stroke rate will be displayed separately by gender (male/female), AF type (persistent/long-standing persistent), age (≤ 70 years, >70 years), and region (US/non-US). Due to the small number of expected peri-procedural strokes, the study is not powered for these subgroup analyses, however, for these analyses, point estimates and exact one-sided 95% upper confidence intervals will be computed within each subgroup.

12.2.10 Analysis Timing

A visit cutoff date will be defined as the maximum of the last 6-month post-index ablation visit, last study exit, or last 30-day post-reablation procedure visit. The data from all visits and procedures meeting this visit cutoff date will be included in the analysis.

12.3 Secondary Objectives

12.3.1 Secondary Objective #1: 6-month Post-Procedural Effectiveness

12.3.1.1 Objective

Confirm the 6-month post-procedural effectiveness.

12.3.1.2 Hypothesis

There is no pre-specified hypothesis associated with this secondary objective.

Since the 6-month effectiveness of the Phased RF system was shown to be superior to optimal medical management in the TTOP-AF study and the primary purpose of this study is to evaluate the safety of the system there is no formal statistical hypothesis required for this objective. Thus, the main purpose for characterizing 6-month effectiveness is to demonstrate that study investigators are not overly cautious during the Phased RF procedure to optimize procedure safety.

12.3.1.3 Definition of 6 Month effectiveness

6-Month effectiveness will be defined as:

- Acute procedural success, AND
- $\geq 90\%$ reduction in clinically significant AF/AFL by 48-hour ambulatory ECG monitor. Clinically significant AF/AFL is defined as; any AF/AFL episode lasting longer than 10 consecutive minutes in duration, AND
- Off amiodarone for at least 90 days and off all other class I and class III antiarrhythmic drugs for at least 60 days prior to the 6-month ambulatory ECG monitor, AND
- Free from DC cardioversion for AF for at least 60 days prior to the 6-month ambulatory ECG monitor

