- Antiplatelet agents
- Angiotensin-converting enzyme (ACE) inhibitors
- Angiotensin-II receptor blockers (or inhibitors), also known as ARBs
- Antiarrhythmic drugs (AADs)
- Beta blockers
- Calcium channel blockers
- Diuretics
- Vasodilators
- Digitalis preparations
- Statins

Therapeutic anticoagulation: Therapeutic anticoagulation is defined as an INR of 2.0 to 3.5. All subjects are required to be prescribed to a vitamin K antagonist (VKA) 30 days prior to the ablation procedure to achieve therapeutic anticoagulation. Subjects will then be required to stay on a VKA for the remainder of their study participation.

Antiarrhythmic Drug (Class I and III) and Direct Cardioversion Use: All subjects will be allowed to be prescribed to one or more class I and/or III antiarrhythmic drug and undergo direct cardioversion as described in Table 8 below.

Table 8: Class I and III Antiarrhythmic Drug Use Intervals

AAD & DC Cardioversion	Use Intervals	
Amiodarone	Allowed; Baseline to 3 month visit	Not allowed within 90 days prior to 6-month Holter *
Class I and III AADs	Allowed; Baseline – 4 months	Not allowed within 60 days prior to 6-month Holter*
DC cardioversions	Allowed; Baseline – 4 months	Not allowed within 60 days prior to 6-month Holter*

*For patient safety and welfare, investigators are allowed to prescribe the use of AAD or DC Cardioversions if medically necessary during “not allowed” use intervals. However, this will be considered a protocol deviation.

History of Atrial Fibrillation: At the time of enrollment, the investigators are required to indicate in the subjects' medical record whether the existing atrial fibrillation is persistent or long-standing persistent as defined in the inclusion criteria. In addition, the subject will be required to complete a 48-hour ambulatory ECG monitor at the baseline visit to demonstrate persistent AF at the time of enrollment.

Arrhythmic symptom review: Subjects will be queried to determine what symptoms if any, they are experiencing due to atrial fibrillation at protocol defined clinic visits and unscheduled clinic visits.

12 Lead ECG: Will be collected at protocol defined study visits and unscheduled study visits to determine heart rhythm along with specific intervals. The Baseline 12 lead ECG should be completed within the 3 months prior to the index ablation procedure.

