Cardioversion Log: At protocol defined study visits and unscheduled study visits the cardioversion log will be updated with the date of any electrical cardioversions that have been performed since last clinic visit.

48-hour ambulatory ECG monitor: Will be collected at protocol defined study visits to determine heart rhythm. Examples of ambulatory ECG monitors are Holter monitors, wearable wireless adhesive ECG monitors (e.g. ECG patch monitors).

For the Baseline ambulatory ECG monitoring, this should be completed within the 3 months prior to the index ablation procedure to document study subject has continuous AF. Subjects may be asked to repeat an ambulatory ECG monitoring session if less than 24 hours of analyzable monitoring time is obtained or continuous AF is not demonstrated. The ambulatory ECG monitoring technology used at the 6-month visit should be the same as the technology used at the baseline visit.

Trans-thoracic echocardiogram (TTE): Will be collected at Baseline or within previous 6 months of the index or reablation procedure to determine atrial volume and size.

Trans-esophageal echocardiogram (TEE): Will be collected within 48 hours prior to the index or reablation procedure to rule-out left atrial thrombus.

If a left atrial thrombus is visualized during pre-procedure TEE, the study subject will not undergo the study ablation procedure at that time.

MRI/CT scan (Chest): Will be done prior to ablation procedure and 3 months post index ablation procedure for the assessment of PVS in subjects in the PVS assessment cohort.

For the Baseline scan, this should be completed within the 3 months prior to the index ablation procedure.

The imaging technology (MRI, CT) used at Baseline pre-procedure scan must match the 3-Month post-procedure scan technology for a given study subject.

International normalized ratio (INR): Blood will be drawn at each study visit (i.e. within the study visit window) to determine the subject's INR.

Two (2) INR levels demonstrating the study subject is therapeutic on VKA are required in the 30 days prior to the index ablation procedure. INR draws from other health care providers are permitted.

Esophagus visualization: Perform visualization prior to ablation procedure using site standard procedure.

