12.3.1.4 Analysis Methods

Acute effectiveness for each subject will be determined as described in section 12.3.2. In order for a subject to meet the acute procedural success criterion for the 6-month effectiveness endpoint, the subject must be an acute procedural success for their index and reablation procedure (if required). Ambulatory ECG monitor recordings will be completed at the baseline and 6-month post final Phased RF ablation visit. Ambulatory ECG recordings will be read and summarized by the Holter core laboratory. For the baseline and 6-month post-ablation procedure ambulatory ECG recording, the percentage of time in clinically significant AF (AF > 10 minutes) will be calculated as the total number of seconds in clinically significant AF divided by the total analyzable ambulatory ECG monitor recording time in seconds. The percent reduction from baseline will be calculated as the difference of the percentage of time in clinically significant AF between the baseline and 6-month post-ablation procedure visit divided by the percentage of clinically significant AF at baseline. Subjects with at least a 90% reduction in clinically significant AF will be considered successful for the ambulatory ECG component of 6-month effectiveness endpoint. Adjustments to all cardiovascular medications including antiarrhythmic drugs and dates of all DC Cardioversions will be captured on the case report forms.

Only those subjects that have a baseline and 6-month post-procedure 48-hour ambulatory ECG monitor data that are readable by the core lab or are missing ambulatory ECG data but were 6-month effectiveness failures based on other criteria at the time of the visit cutoff date will be included in the analysis of this

objective. Specifically, the denominator for the 6-month effectiveness rate will include all subjects that had at least one Phased RF ablation procedure where an investigational catheter was deployed into the left atrium and have baseline and 6-month ambulatory ECG monitor data available or do not have ambulatory ECG data available but were 6-month effectiveness failures based on other criteria. The numerator will include all subjects in the denominator that meet all four 6-month effectiveness conditions. A two-sided 95% exact confidence interval for 6-month effectiveness rate will be calculated.

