### 3.3.1.2 Definition of 6 Month Effectiveness

6-Month effectiveness will be defined as:

- Acute procedural success, AND
- $\geq 90\%$  reduction in clinically significant AF/atrial flutter (AFL) by 48-hour Holter. Clinically significant AF/AFL is defined as any AF/AFL episode lasting longer than 10 consecutive minutes in duration, AND
- Off amiodarone for at least 90 days and off all other class I and class III antiarrhythmic drugs for at least 60 days prior to the 6-month Holter, AND
- Free from direct current (DC) cardioversion for AF for at least 60 days prior to the 6-month Holter

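### The 6-month effectiveness definition fails a subject only for DC cardioversion for AF, so one done for atrial flutter inside the 60-day window does not count against success

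*Protocol*

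**What the plan says.** Success at 6 months needs four conditions together. The fourth, in protocol 12.3.1.3, is "Free from DC cardioversion for AF for at least 60 days prior to the 6-month ambulatory ECG monitor". Protocol 1.9 and 6.2.2.1 say the same, and SAP 3.3.1.2 has "Free from direct current (DC) cardioversion for AF for at least 60 days prior to the 6-month Holter".

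Other parts of the plan treat the rhythm differently:

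- The second condition of the same definition covers both rhythms: "Clinically significant AF/AFL is defined as; any AF/AFL episode lasting longer than 10 consecutive minutes in duration".
- Reablation (protocol 7.15) is triggered by "Recurrent AF/AFL that cannot be controlled with antiarrhythmic drugs and/or cardioversion".
- Table 8 in protocol 7.7 has a row for DC cardioversions with no rhythm named: "Not allowed within 60 days prior to 6-month Holter". Its footnote permits a medically necessary cardioversion in that interval and classes it as a protocol deviation. It does not mention effectiveness failure.
- The burden calculation in protocol 12.3.1.4 drops flutter: "the percentage of time in clinically significant AF (AF > 10 minutes) will be calculated". SAP 3.3.1.3 does the same.

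On data, protocol 7.7 says "the cardioversion log will be updated with the date of any electrical cardioversions that have been performed since last clinic visit", and 12.3.1.4 states that the dates of all DC cardioversions go on the case report forms.

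**The concern.** The 60-day condition is there so that a 48-hour recording reflects the ablation and not a recent shock. Flutter counts as recurrence on the monitor, so a shock that ends flutter can clean up the recording just as one that ends AF can. The written condition catches only the second.

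The rate goes into the PMA report, and its stated purpose (protocol 12.3.1.2) is to show that operators did not hold back during the procedure for the sake of safety. Successes that owe something to a late cardioversion weaken that reading, and the error runs in one direction only. Two analysts could also score the same subject differently, because the text does not say which record decides whether a cardioversion was for AF.

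**Working it through.** **1. One subject followed through the rules.** Take a subject in persistent flutter who is electrically cardioverted on day 175 and monitored from day 180, with acute success, the drug-free intervals met and a clean recording.

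| Rule | Result |
|---|---|
| Acute success | met |
| At least 90% reduction on the monitor | met |
| Off amiodarone 90 days, other class I/III drugs 60 days | met |
| No DC cardioversion for AF in 60 days | met, because the rhythm treated was flutter |
| Table 8 | breached, recorded as a deviation |
| Score (12.3.1.4: all four conditions) | success |

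**2. The same subject without usable monitor data.** Protocol 12.3.1.4, 12.3.1.5 and 12.3.1.7 admit a subject with missing monitor data only if another criterion has already failed. Under the literal wording none has, so the subject leaves the denominator. If the 6-month visit was completed, the subject enters the tipping-point analysis as a success and is only then switched to failure in the iterations.

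**3. What the word AF could mean.**

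| Reading | Flutter on the monitor | Flutter cardioversion | Outcome |
|---|---|---|---|
| AF stands for AF/AFL throughout | counts | counts | no gap |
| As the definition is written | counts | does not count | the shock can create a success |
| AF literal throughout, including the burden formula | does not count | does not count | flutter can pass with or without a shock |

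Only the first reading closes the gap.

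**4. Reproducing the plan's precision figures.** The inputs from protocol 12.3.1.6 are n = 200, an observed rate of 55% or 50%, and an exact two-sided 95% interval. For x successes, the lower limit is the 0.025 quantile of Beta(x, n − x + 1) and the upper limit is the 0.975 quantile of Beta(x + 1, n − x).

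- 110/200: 47.82% to 62.02%, width 14.20 (plan: 47.8%, 14.2).
- 100/200: 42.87% to 57.13%, width 14.27 (plan: 42.9%, 14.3).

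Both agree. No figure in the plan is disputed.

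**5. Effect of rescoring.** Moving one subject from success to failure with n fixed changes the rate by 1/200 = 0.5 points. The numbers moved below are assumptions.

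| Subjects moved | Rate | Exact 95% CI |
|---|---|---|
| 0 | 110/200 = 55.0% | 47.8% to 62.0% |
| 1 | 109/200 = 54.5% | 47.3% to 61.5% |
| 2 | 108/200 = 54.0% | 46.8% to 61.1% |
| 4 | 106/200 = 53.0% | 45.8% to 60.1% |
| 10 | 100/200 = 50.0% | 42.9% to 57.1% |

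Restoring one dropped subject as a failure gives 110/201 = 54.7%, a fall of about 0.3 points.

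**The case against.** **AF may be shorthand for both rhythms.** The analysis sections do use AF where the definition says AF/AFL, so this is possible. It does not remove the problem, because the definition itself uses AF/AFL in one condition and AF in another. If AF is instead literal everywhere, flutter escapes the burden formula too. The objection does show that the wording of the burden calculation belongs in the same correction.

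**Table 8 is a conduct rule.** This stands. A reader might infer that Table 8 and the endpoint contradict each other. They do not: a deviation need not be an endpoint failure, and which cardioversions void success is partly a design choice. The mismatch that matters is inside the definition.

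**The data may well allow the distinction.** A reader might infer that the log holds dates only, so that the AF qualifier cannot be applied. The documents do not support that. They say dates are captured, not that nothing else is. The case report form is not in the documents and may record the rhythm. Visits include a 12-lead ECG and cardioversion history, and deviations must be recorded with an explanation (Table 15). Part of SAP 3.3.1.3 is also blacked out. What stands is that no visible text says which record decides.

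**The effect is small and its total unknown.** This stands. No flutter-cardioversion rate is given, and such a subject must also meet the other three conditions. Study success rests on stroke alone.

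**Conclusion.** The point holds as a minor defect in the definition. Followed literally, it counts as a success a subject cardioverted from flutter inside the window who meets the other three conditions, and it drops such a subject when monitor data are missing and nothing else has failed. Both effects can only raise the reported rate.

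The size is 0.5 points per rescored success at 200 evaluable subjects, against an interval about 14 points wide. Under an assumed 55%, it would take ten such subjects (10/200 = 5%) to reach the 50% that the plan expects to exceed. Nothing in the documents shows that number to be likely, so a reader should not infer a known inflation of the rate.

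The objective has no hypothesis (protocol 12.3.1.2). The primary stroke endpoint, its type I error and its power do not depend on it.

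**What to change.** - In protocol 1.9, 6.2.2.1 and 12.3.1.3 and in SAP 3.3.1.2, score any DC cardioversion for AF or AFL in the 60 days before the 6-month monitor as an effectiveness failure.
- Count a cardioversion with no recorded rhythm as AF/AFL, and name the record that decides the rhythm.
- Use AF/AFL consistently in the burden calculation (protocol 12.3.1.4, SAP 3.3.1.3).
- Add a sensitivity analysis that fails every DC cardioversion in the window. This one follows Table 8's unqualified wording, which the AF-or-AFL rule does not fully match, and it needs only the recorded dates.

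If the limit to AF is deliberate, the plan should say so and state who classifies each cardioversion and from what record; the sensitivity analysis is then still needed.

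These changes concern scoring only and leave the treatment rules in Table 8 alone. The cost is a few words in each place and one extra analysis, with no new visits. The downside is that the reported rate may fall slightly, and a cardioversion of unrecorded rhythm that was for something else would be counted as a failure.
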